9.8 Data Management

Survey data collection will be completed on-line in Conformat, a software platform specifically designed for the creation and delivery of multi-lingual surveys. Data collected will be stored at secure servers and will be maintained to ensure compliance with applicable local and national regulations.

Response sets for multiple-choice questions will be randomised to minimise bias. To minimise likelihood that respondents would look up answers and/or discuss the survey while taking it, respondents will be asked to complete survey in 1 sitting and will not be allowed to revise their answers after they advance to the next question.

Survey database lock is anticipated to occur shortly after the survey is closed in all countries. To reduce opportunity for bias, survey respondents will not be contacted to clarify or revise their responses to knowledge assessment-related questions.

Data management will be in accordance with the ICON's standard operating procedures (SOPs). Additional details regarding data collection, management of missing data, data storage, and validation procedures will be detailed in the survey manual and statistical analysis plan (SAP).

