Annex 3: Survey questionnaire

Please enter your Unique ID to participate in the survey. Your Unique ID was provided in your survey invitation.

Unique ID: **→ IF ENTERED, PROCEED TO COUNTRY AND LANGUAGE SELECTION, OTHERWISE, TERMINATE SURVEY**

The above section will only appear for respondents who did not receive their invitation directly by email from the Conformat survey software.

Surveys invitations will include a unique ID for each HCP which will need to be entered to access the survey.

Include a % Completed Bar at the top of the survey for respondents.

Correct responses are ticked as ✓ and will be removed for the actual survey.

Please select your country and language from the list below:

- Austria (German) → **PROCEED TO SURVEY INTRODUCTION**
- Germany (German) → **PROCEED TO SURVEY INTRODUCTION**
- Italy (Italian) → **PROCEED TO SURVEY INTRODUCTION**
- The Netherlands (Dutch) → **PROCEED TO SURVEY INTRODUCTION**
- My country is not listed → **THANK AND TERMINATE**

[Termination Language for Non-Qualified Candidates:]

Thank you for your interest in participating in this survey. However, we are required to limit participation to healthcare professionals who are from 1 of the 4 listed countries. We look forward to your potential participation in a future survey.

Survey Introduction

On behalf of Genzyme Europe BV (Sanofi), ICON is conducting a survey among healthcare professionals who prescribe ENJAYMO™ (sutimlimab). **Sanofi is required to perform this survey as mandated by the European Medicines Agency (EMA) in line with the ENJAYMO™ (sutimlimab) Risk Management Plan for Europe.** The overall goal of this study is to evaluate the effectiveness of the “**ENJAYMO™ Physician’s Guide.**” Participation in this survey is voluntary and will not affect your ability to prescribe ENJAYMO™.

The survey is expected to take up to 20 minutes to complete and is recommended to be completed in one sitting.

To complete the survey, you must meet study eligibility criteria. Please be assured that your individual answers will be held confidential. This study will summarise aggregated results provided by all participating healthcare professionals in order to protect the confidentiality of your individual answers.

By participating, you agree that ICON may contact you only in reference to this survey. You may withdraw from the survey at any time, in which case the information you have already provided will not be used in the final study report.

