Please click on the NEXT button to verify that you qualify for this survey and to complete the required documentation for participation.

[BEGIN SURVEY SCREENING QUESTIONS]

S1. Does your practice include patients with cold agglutinin disease?

- Yes → **PROCEED TO S2**
- No → **PROVIDE A POP-UP THAT STATES** “Based on your answer, you are not eligible to take this survey. Please click “Next” to confirm your answer is correct, or click “Back” to review your answer”. **IF THE USER CLICKS ON ‘BACK’ THEN THE QUESTION WILL BE DISPLAYED AND THE RESPONSE CAN BE**

CHANGED. IF THE USER CLICKS ON ‘NEXT’ THEN THANK AND TERMINATE.

- S2. Do you provide your permission to share your anonymized survey responses, aggregated with all other survey responses, with the European Medicines Agency or national competent authorities?
- Yes → **PROCEED TO S3**
 - No → **PROVIDE A POP-UP THAT STATES** “Based on your answer, you are not eligible to take this survey. Please click “Next” to confirm your answer is correct, or click “Back” to review your answer”. **IF THE USER CLICKS ON ‘BACK’ THEN THE QUESTION WILL BE DISPLAYED AND THE RESPONSE CAN BE CHANGED. IF THE USER CLICKS ON ‘NEXT’ THEN THANK AND TERMINATE.**
- S3. Are you or have you been a direct employee of Sanofi, ICON, the European Medicines Agency, or other European-based National Competent Authorities within the past 5 years?
- Yes → **PROVIDE A POP-UP THAT STATES** “Based on your answer, you are not eligible to take this survey. Please click “Next” to confirm your answer is correct, or click “Back” to review your answer”. **IF THE USER CLICKS ON ‘BACK’ THEN THE QUESTION WILL BE DISPLAYED AND THE RESPONSE CAN BE CHANGED. IF THE USER CLICKS ON ‘NEXT’ THEN THANK AND TERMINATE.**
 - No → **PROCEED TO MAIN SURVEY**

[Termination Language for Non-Qualified Candidates:]

Thank you for your interest in participating in this survey. However, we are required to limit participation to healthcare professionals who meet the survey eligibility requirements. We look forward to your potential participation in a future survey.

[Language for Qualified Candidates:]

Thank you for your responses. You qualify for this survey, and we look forward to your participation. Once you enter the main survey, you will only be able to move forward through the questions.

[END SURVEY SCREENING QUESTIONS]

MAIN SURVEY

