[Preamble 1]: These questions are about the risks of serious infections and meningococcal infections associated with ENJAYMO™ (sutimlimab). Please be sure to review all response choices for each question before answering each question. Please note that you will only be able to move forward in the survey as you complete each question.

CORRECT RESPONSES ARE CHECKED ✓

1. Did you receive the “ENJAYMO™ Physician’s Guide” that provides information to minimise the risks of serious infections and meningococcal infections associated with product use?
 - Yes
 - No
 - I don’t know/am not sure

2. Did you read the “ENJAYMO™ Physician’s Guide” that provides information to minimise the risks of serious infections and meningococcal infections associated with product use?
 - Yes
 - No
 - I don’t know/am not sure

3. ENJAYMO™ (sutimlimab) is indicated in adult patients with cold agglutinin disease (CAD) for the treatment of (Check all that apply) **RANDOMIZE ORDER OF THE FIRST 5 RESPONSES**
 - Hemolytic anaemia
 - Jaundice
 - Cardiac arrhythmia
 - Nausea and vomiting
 - Cold agglutinin syndrome
 - I don’t know/am not sure

4. ENJAYMO™ (sutimlimab) should only be prescribed to patients who have received appropriate vaccinations, especially against encapsulated bacteria.
 - True
 - False
 - I don’t know/am not sure

5. Are you familiar with current local guidelines or recommendations in patients with persistent complement deficiencies for meningococcal conjugate vaccine(s), meningococcal serogroup B vaccine(s), and pneumococcal vaccine(s)?

Yes
 No
 I don't know/am not sure

6. According to the ENJAYMO™ (sutimlimab) **Summary of Product Characteristics** and the “**ENJAYMO™ Physician’s Guide**”, which of the following warrant specific caution when using ENJAYMO™ (sutimlimab)? Please select all that apply.

Neisseria meningitides infection
 Hemophilus influenza infection
 Streptococcus pneumoniae infection
 Urinary tract infection
 All of the above
 I don't know/am not sure

7. According to the “**ENJAYMO™ Physician’s Guide**”, which of the following are important activities that are necessary when using ENJAYMO™ (sutimlimab):

		Yes, needs to be monitored	No, does not need to be monitored	I don't know/am not sure
A	Monitor patients for kidney damage			

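### The two stated measures against look-up do not act before an answer is given; the questionnaire shown neither asks for answers from memory nor records whether a source was consulted, and section 9.11 omits the upward bias

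*Protocol*

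**What the plan says.** Section 9.8 (Data Management) states its aim, "To minimise likelihood that respondents would look up answers and/or discuss the survey while taking it", and gives two measures in the same sentence: "respondents will be asked to complete survey in 1 sitting", and respondents "will not be allowed to revise their answers after they advance to the next question". Randomised response order is mentioned separately, as a measure against bias in general: "Response sets for multiple-choice questions will be randomised to minimise bias".

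Annex 3 carries both measures into the questionnaire. The introduction says "The survey is expected to take up to 20 minutes to complete and is recommended to be completed in one sitting". The text shown to qualified candidates says "Once you enter the main survey, you will only be able to move forward through the questions", and Preamble 1 repeats it: "Please note that you will only be able to move forward in the survey as you complete each question". Apart from that, Preamble 1's only guidance on how to answer is "Please be sure to review all response choices for each question before answering each question", which concerns reading the options and not the use of sources.

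Section 9.2.1 defines the primary endpoint as a composite knowledge level over questions 3 to 8, with success at 80% or more if at least 30 HCPs answered. Section 9.9.1.2 stratifies knowledge by whether the Guide was read. Section 9.11 discusses selection, social desirability and recall bias. It does not mention look-up.

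**The concern.** The protocol itself recognises look-up as a threat to a knowledge endpoint, yet its measures act at the wrong moment. Forward-only navigation blocks the correction of earlier answers. It does not block reading a source before answering the current question. A single sitting discourages breaks, not a second browser window.

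The wording of the questionnaire adds to the exposure. Questions 6, 7 and 8, half of the core set, ask what the Guide says, and question 6 also names the SmPC. The main recruitment lists are of HCPs who were sent the Guide. Since nothing in the text shown asks for unaided answers, a conscientious respondent could take the survey to be open-book.

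Two results are at stake. Consulting the Guide mainly turns wrong answers into right ones, so the composite moves towards 80%. The contrast between readers and non-readers also shrinks, because a non-reader who opens the Guide during the survey scores as knowledgeable.

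**Working it through.** **1. The plan's own figure.** Inputs from section 9.7: n = 50, knowledge 80%, 95% two-sided interval, simple asymptotic formula.

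Half-width = 1.96 × √(0.80 × 0.20 / 50) = 1.96 × 0.0566 = 0.1109, or 11.1 points (68.9% to 91.1%). This reproduces the protocol. It is sampling error only; a systematic shift from look-up lies outside it.

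**2. What each measure reaches.**

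| Measure | Stops a later change to an earlier answer | Stops consulting a source before answering |
|---|---|---|
| Single sitting (requested) | No | No |
| No revision after advancing | Yes | No |

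The protocol and Annex 3 state no time limit per question and no supervision. None of questions 1 to 21 asks whether a source was consulted.

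**3. Which core questions are exposed.** Questions 3, 4, 6, 7 and 8 have a factual answer. Question 5 asks whether the HCP is familiar with local vaccination guidance, so there is no fact to look up. Five of the six are exposed.

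**4. Size, as an illustration.** The documents give neither true knowledge k nor the share f of respondents who look up, so both are assumed. Further assumptions: the six questions carry equal weight and start at the same level k; those who look up have average knowledge to begin with, reach 100% on the five exposed questions and are unchanged on question 5.

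Observed level = k + f × (5/6) × (1 − k)

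Share needed for an observed 80%: f = (0.80 − k) / [(5/6) × (1 − k)]

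- k = 60%: 0.20 / (0.8333 × 0.40) = 0.60
- k = 70%: 0.10 / (0.8333 × 0.30) = 0.40
- k = 75%: 0.05 / (0.8333 × 0.25) = 0.24

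For smaller and larger f at k = 70%, each 10% of respondents who look up adds 0.10 × 0.8333 × 30 = 2.5 points. So f from 10% to 50% gives an observed level from 72.5% to 82.5%.

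**5. What a sensitivity analysis would leave.** If everyone who looked up said so, 50 × (1 − f) respondents remain: 20 at f = 60%, 30 at f = 40% and 38 at f = 24%. The first falls below the protocol's floor of 30 and the second just meets it.

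**The case against.** Several points on the other side are fair.

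- Section 9.8 promises to reduce the likelihood of look-up, not to exclude it, and any unsupervised online survey shares the problem. This stands: the protocol makes no false claim here.
- A reader might infer that a single sitting is the only safeguard. It is not. The same sentence bars revision, and Annex 3 applies that bar.
- A reader might see a contradiction between asking for one sitting in section 9.8 and recommending it in Annex 3. Both are non-binding requests, and neither wording affects look-up within the session.
- Applying look-up to all six questions would give lower required shares of 50%, 33% and 20%. That overstates the effect, because question 5 cannot be looked up.
- The invitation letter, the online agreement, the survey manual and the SAP are not shown, and a request to answer unaided could stand in one of them. This limits the claim to the text shown. It does not remove it: the questions are in Annex 3, and no SAP can analyse an item that they do not collect.
- The survey is descriptive, with no prior hypothesis. It nevertheless assesses its composite against a stated 80%, so a one-directional error still affects the reading.

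**Conclusion.** The concern holds as a gap between a stated aim and the means chosen. Neither measure in section 9.8 acts before the answer is given, the questionnaire shown does not ask for unaided answers or record the use of sources, and section 9.11 leaves out a bias that runs towards success.

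Its actual size is unknown. Under the assumptions in the working, 60%, 40% or 24% of respondents would have to look up for true knowledge of 60%, 70% or 75% to appear as 80%. Large shares are needed unless true knowledge is already close to the target. If look-up corrects fewer answers, the shares needed are higher; if those who look up know less than average, the shares are lower.

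The documents do not support saying that look-up will be common or that the primary result will be invalid. This is a cheap improvement worth making before the survey opens, since the missing item cannot be recovered afterwards.

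**What to change.** 1. Add to Preamble 1 an instruction to answer from current knowledge, without consulting the Guide, the SmPC, the internet or colleagues.
2. Add one unscored closing item asking whether any source was consulted while answering (yes or no).
3. Report the composite again without those who answer yes, as a descriptive sensitivity analysis, and assess it against 80% only if at least 30 respondents remain.
4. Name look-up in section 9.11 as a limitation, with its direction.

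Cost: one sentence, one question, their translation for the participating countries, and one further run of the composite. The survey becomes slightly longer. The closing item is self-reported and will miss some look-up, for the social-desirability reason that section 9.11 already gives. The sensitivity analysis rests on fewer respondents: with 30 left and 80% correct, the half-width is 1.96 × √(0.16 / 30) = 14.3 points, against 11.1 at 50. Those excluded may also differ in knowledge from those who remain, so the re-run shows how far the result depends on them and is not a corrected estimate.

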9.9 Data Analysis

9.9.1 Statistical Analysis

All analyses will be performed by ICON Plc.

A SAP will be developed and will describe all planned analyses in detail, along with any specifications for tables, listings, and figures to be produced. The SAP will be finalized prior to database close. Any changes to analyses outlined in the SAP will be captured in the final study report as changes to the SAP.

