All data will be maintained in compliance with local regulations. Results will be analyzed using SAS. Results will be summarized in tables and figures (as applicable). A statistical analysis plan will be developed to describe the planned statistical analyses in detail and finalized prior to the end of data collection. A final study report will be prepared.

Population:**Inclusion criteria:**

1. Prescribers, and potential prescribers, of ENJAYMO™.
2. Provides permission to share their responses in aggregate with EMA or national competent authorities, if requested

Exclusion criteria:

1. Is or has been a direct employee of Sanofi, the EMA, or ICON plc within the last five years.

Variables:Primary endpoint

The primary endpoint is knowledge levels of key information included in the ENJAYMO™ Physician's Guide across these 4 domains:

- Indication for CAD patients only
- Important potential risks of serious infections and meningococcal infections
- Recommendations for vaccination of patients as per local regulations
- Recommendations for monitoring and counseling patients to promote real-world safe-use conditions.

The primary endpoint is a composite endpoint based on the percentages of HCPs with correct responses to questions included in the composite. The composite is the weighted average knowledge level across the core question set (6 questions) from the above domains. Success criteria for the primary endpoint percentage is at least 80% of HCPs have answered the item correctly (if the number of HCPs who answered is at least 30).

Secondary endpoints

- The distribution of HCPs' reported levels of receipt and reading of the ENJAYMO™ Physician's Guide,

- HCPs' knowledge levels for each question regarding the information included in the ENJAYMO™ Physician's Guide (i.e., all questions relating to all domains), assessed as the percentages of HCPs with correct responses to each question,
- The distribution of HCP's reported levels of dissemination of the ENJAYMO™ Patient Guide to patients treated with ENJAYMO™ (questions asked to ENJAYMO™ prescribers only),
- The distribution of HCPs' responses regarding their experience with patients' receptivity to vaccination (questions asked to ENJAYMO™ prescribers only),
- Implementation of vaccination (questions asked to ENJAYMO prescribers only), and
- The distribution of responses regarding the primary source(s) from which HCPs learned about the information included in the ENJAYMO™ Physician's Guide.

Other endpoints

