6 MILESTONES

The survey is planned to launch no sooner than 6 months, and no later than 18 months after the ENJAYMO™ Physician's Guide has been disseminated in each participating country. The study milestones below are as follows:

Milestone	Planned periods
EMA protocol submission	Q2 2022
Registration in the EU PAS register	Prior to start of data collection
Start of data collection	Q2 2024*
End of data collection	Q4 2025*
Final report of study results	Q1 2026*

*Dependant on launch dates

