9.3 Study Design

This is a multinational, non-interventional, cross-sectional survey study to evaluate the effectiveness of the ENJAYMO™ Physician's Guide among EEA-based HCPs.

The current study is planned to be conducted among HCPs in countries in the EEA where the product is expected to be commercially available for at least 6 months. The survey will be launched no sooner than 6 months, and no longer than 18 months, after the ENJAYMO™ Physician's Guide has been disseminated in each participating country. Countries may include Austria, Germany, Italy, and the Netherlands. A convenience sample of HCPs will be recruited from the target population of HCPs who treat patients with CAD and may prescribe ENJAYMO™ in these countries.

The survey is anticipated to be open between 3 to 6 months per country per wave. Depending on response rates, follow-up reminders will be sent to non-respondents to endeavor to achieve the target sample size, and the medical scientific liaison team of Sanofi may also be involved in some countries to advocate for the participation in the survey through their personal contacts with HCPs already contacted via e-mail. In the event that less than 30 completed surveys are achieved in the first wave of the study, a second wave of the same survey will be triggered.

Data will be collected by web-based electronic data capture. Information collected will include the receipt and reading of the ENJAYMO™ Physician's Guide, knowledge of the key information included in the ENJAYMO™ Physician's Guide, the impact of the ENJAYMO™ Physician's Guide on clinical action, and HCP characteristics.

All data will be maintained in compliance with local regulations. Results will be analyzed using SAS. Results will be summarized in tables and figures (as applicable). A statistical analysis plan will be developed to describe the planned statistical analyses in detail and finalized prior to the end of data collection. A final study report will be prepared.

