9.9.1.1 Analysis Populations

The primary analysis population will include all HCPs who have completed at least 1 of the primary effectiveness endpoint questions in the survey. Denominators used to calculate knowledge levels for individual survey questions will reflect the number of respondents who completed the particular survey question including responses of 'I don't know/not sure'.

In the event that the study is conducted in 2 waves, HCP responses from both waves will be combined to comprise the primary analysis population.

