1.1.3 Progress report(s)				
1.1.4 Interim report(s)				
1.1.5 Registration in the EU PAS Register®				
1.1.6 Final report of study results.				

¹ Date from which information on the first study is first recorded in the study dataset or, in the case of secondary use of data, the date from which data extraction starts.

² Date from which the analytical dataset is completely available.

Comments:

--

Section 2: Research question	Yes	No	N/A	Section Number
2.1 Does the formulation of the research question and objectives clearly explain:				
2.1.1 Why the study is conducted? (e.g. to address an important public health concern, a risk identified in the risk management plan, an emerging safety issue)				7
2.1.2 The objective(s) of the study?				8
2.1.3 The target population? (i.e. population or subgroup to whom the study results are intended to be generalised)				9.4
2.1.4 Which hypothesis(-es) is (are) to be tested?				
2.1.5 If applicable, that there is no a priori hypothesis?				8

Comments:

--

Section 3: Study design	Yes	No	N/A	Section Number
3.1 Is the study design described? (e.g. cohort, case-control, cross-sectional, other design)				9.3
3.2 Does the protocol specify whether the study is based on primary, secondary or combined data collection?				9.1, 9.8
3.3 Does the protocol specify measures of occurrence? (e.g., rate, risk, prevalence)				

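### The SAP may be finalised after most answers are in, while the protocol leaves result-changing scoring choices open

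*Protocol*

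**What the plan says.** The protocol gives the SAP deadline in three places.

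- Section 9.9.1: "The SAP will be finalized prior to database close".
- Section 9.3: a SAP will be written "in detail and finalized prior to the end of data collection".
- Section 4 (synopsis): the same limit, "finalized prior to the end of data collection".

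Two further statements show where these limits fall. The checklist in Annex 4 defines the end of data collection as "Date from which the analytical dataset is completely available". Section 9.8 says: "Survey database lock is anticipated to occur shortly after the survey is closed in all countries".

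Section 6 plans data collection from Q2 2024 to Q4 2025, depending on launch dates. There may be up to two waves, the second opening 6 to 12 months after the first closes (synopsis). On their use, section 9.9.1.1 states: "In the event that the study is conducted in 2 waves, HCP responses from both waves will be combined to comprise the primary analysis population".

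Section 9.9.1 also requires changes to the analyses in the SAP to be recorded in the final study report.

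**The concern.** Finalising a SAP before database lock is ordinary practice and is usually harmless when blinding hides the result. This survey has no such protection. There is one group and the answer key is in the protocol, so stored answers can be scored at once and compared with 80%.

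Late finalisation would still matter little if the protocol fixed the decision completely, but it does not. Some choices that determine the composite and the success call are left to be settled. If they are settled once answers can be read, a pass cannot be told apart from a rule chosen because it passes. The duty to report changes to the SAP does not help here, because a choice made before the SAP is final is not a change to it.

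**Working it through.** **1. Do the deadlines differ in practice?** By wording, the end of data collection comes before database close, so meeting the former meets the latter. By the Annex 4 definition, the end of data collection is when the analytical dataset is complete, and section 9.8 puts lock shortly after the survey closes everywhere. The two limits nearly coincide. Both fall after most answers have been collected and, in a two-wave study, after all of wave 1 and the 6 to 12 month gap.

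**2. What is already fixed?** The six core questions (section 9.2.1), the answer key (Table 9-1 and Annex 3), the 80% threshold and minimum of 30 (sections 9.2.1 and 9.9.1.2), denominators that include don't-know answers (section 9.9.1.1), opportunity-based weighting and no imputation (section 9.9.1.2), and pooling of waves (section 9.9.1.1).

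**3. What is contradictory or open?**

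- The data analysis part of the synopsis assesses HCPs who got all the core questions right. Sections 9.2.1 and 9.9.1.2 speak of each item.
- Section 9.2.1 counts six questions, while Table 9-1 lists the parts of the multi-part questions separately. Whether questions 3, 6, 7 and 8 score per sub-item or all-or-none is not stated.
- Section 9.9.1.2 compares the composite with 80% (± 95% CI) but does not say whether the point estimate or a confidence limit decides.

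**4. The plan's own figure.** Section 9.7 gives a precision of 11.1% for 50 HCPs at 80%. The simple asymptotic half-width is 1.96 × √(0.80 × 0.20 / 50) = 0.1109, with interval 68.9 to 91.1%. The figure is reproduced.

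**5. Effect of the scoring unit (illustration, assumed inputs).** The questionnaire gives 5 + 1 + 1 + 4 + 6 + 6 = 23 sub-items for questions 3 to 8, leaving out the don't-know options and the catch-all option of question 6. Assume each sub-item is answered correctly by 90% of HCPs.

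- Sub-item average: 90%, above 80%.
- All-or-none per question, independent answers: (0.9⁵ + 0.9 + 0.9 + 0.9⁴ + 0.9⁶ + 0.9⁶) / 6 = (0.590 + 0.900 + 0.900 + 0.656 + 0.531 + 0.531) / 6 = 0.685, below 80%.
- All-or-none, latent correlation 0.5 (simulated): about 0.77, below 80%.

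Under independence, the all-or-none average is 57.0% if each sub-item is at 85%, and 82.6% at 95%. At 95% both scorings clear the threshold, so the reversal depends on the level.

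**6. Effect of all questions versus each item (independent answers assumed).** If each of the six questions is 80% correct, the average is 80%, but all six are correct for 0.8⁶ = 26.2%. At 90% the figure is 0.9⁶ = 53.1%.

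**7. Effect of the interval rule.** Take n = 50 and one proportion, as section 9.7 does.

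| Rule against 80% | Smallest passing count | Observed level |
|---|---|---|
| Point estimate | 40/50 | 80% |
| Lower limit | 45/50 | 90% |
| Upper limit | 34/50 | 68% |

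An average over six questions would usually have a narrower interval than one proportion, so the last two cut-offs would move towards 80%. The ordering would stay.

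**8. Is access to answers limited?** No section restricts who may see answers before the SAP is final. Section 9.9.1 assigns all analyses to the vendor, which also runs the survey (Annex 3).

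**The case against.** The strongest case against is that the protocol leaves much less to the SAP than the deadline alone suggests. A reader might infer that the SAP sets the whole deciding rule. Step 2 shows that it does not, and that part of the objection stands.

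A reader might also infer that the scoring will be fixed after wave 1 results are known. The documents do not support this. Annex 4 marks interim and progress reports as not applicable. The trigger for a second wave uses completed surveys and, in section 9.1.1, the number of prescribers. The progress metrics named there are counts, though given as examples. A second wave is itself conditional. That SAP authors could see answers is inferred from the absence of a restriction, and section 9.8 leaves further data-handling detail to the survey manual and the SAP, which are not at hand. This stands against any claim that the look is planned. It does not remove the risk, because nothing in the protocol prevents it.

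It is also fair that the contradictory scoring text is a defect in its own right, which an earlier SAP date would not cure, and that section 8.2 defines no hypothesis. Even so, sections 4 and 9.2.1 declare a success criterion, and the value of that criterion depends on when its rule was settled.

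**Conclusion.** The point holds in limited form. Both stated deadlines allow the SAP to be finalised after most answers are in, and the protocol leaves open three choices that can change the result. With one group, no blinding and no stated access limit, those choices could be made with data in hand. This is a risk the plan allows, not an event it schedules. The difference between the two deadlines is a matter of wording and not a material conflict.

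The illustrative size is 90% against 68.5% (independence) or about 77% (latent correlation 0.5) for the same answers under two scorings. It rests on an assumed 90% for every sub-item, which the documents do not give.

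A reader might want a figure for how far late choice inflates the chance of passing. The documents do not support one. It would need assumed true levels and correlations for rival composites. Treating the composite as one proportion would also overstate its standard error: at a true 75% it is √(0.75 × 0.25 / 50) = 6.1 points, against about 4.0 to 4.7 for a six-question average at inter-item correlation 0.3 to 0.5.

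**What to change.** Replace the sentences in the synopsis, section 9.3 and section 9.9.1 with one rule:

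- The SAP, including the scoring of each core question and the 80% decision rule with the role of the confidence interval, is finalised and dated before the first survey response is collected.
- If that date has passed, it is finalised before any answer data are extracted or viewed, and in any case before wave 1 closes. This fallback is needed because the protocol is dated 05 June 2024 and data collection was planned to start in Q2 2024.
- Until then, only recruitment counts (eligible, ineligible, completed) are released.
- Later changes are reported as post hoc.

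The rule fixes when the choices are made, not which choices. The conflicting scoring sentences in the synopsis and sections 9.2.1 and 9.9.1.2 still have to be reconciled.

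The cost is earlier writing, with no extra data. The small downside is less freedom to adapt the SAP to observed item completion, and such changes can still be made if labelled post hoc.
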